#### 4.2 Ineligibility Criteria

Patients who fulfill any of the following criteria are not eligible for admission to the study:

4.2.1 Prior treatment with a BRAF inhibitor or a MEK inhibitor.

4.2.2 Known ocular or primary mucosal melanoma.

4.2.3 Current use of a prohibited medication as described in Section 7.2.

4.2.4 History of malignancy with confirmed activating RAS mutation at any time. *Note:* Prospective RAS testing is not required. However, if the results of previous RAS testing are known, they must be used in assessing eligibility.

4.2.5 History of malignancy other than disease under study within 3 years of study enrolment, except for patients with a history of completely resected non-melanoma skin cancer, or indolent malignancies such as chronic lymphocytic leukemia are eligible. (*Please call CCTG if any questions about the interpretation of this criterion.*)

ADMIN UPDATE #1: 2017-OCT-03; AMEND #2: 2018-OCT-26

4.2.6 Leptomeningeal metastases or metastases causing spinal cord compression that are symptomatic or untreated or not stable for  $\geq 3$  months (must be documented by imaging). Subjects on a stable dose of corticosteroids  $> 2$  weeks or who have been off of corticosteroids for at least 2 weeks can be enrolled with approval of the CCTG.

4.2.7 Any serious or unstable pre-existing medical conditions (aside from malignancy exceptions specified above), psychiatric disorders, or other conditions that could interfere with the subject's safety, obtaining informed consent, or compliance with study procedures.

4.2.8 A history of Hepatitis B Virus (HBV), or Hepatitis C Virus (HCV) infection (subjects with laboratory evidence of cleared HBV and/or HCV will be permitted).

4.2.9 A history or evidence of cardiovascular risk including any of the following:

- A QT interval corrected for heart rate using the Bazett's formula (QTcB)  $\geq 480$  msec;
- A history or evidence of current clinically significant uncontrolled arrhythmias (*Exception: subjects with atrial fibrillation controlled for  $> 30$  days prior to dosing are eligible*).
- A history of acute coronary syndromes (including myocardial infarction or unstable angina), coronary angioplasty, or stenting within 6 months prior to registration.
- A history or evidence of current  $\geq$  Class II congestive heart failure as defined by the New York Heart Association (NYHA) guidelines;
- Patients with intra-cardiac defibrillators;
- Abnormal cardiac valve morphology ( $\geq$  grade 2) documented by echocardiogram (subjects with grade 1 abnormalities [i.e. mild regurgitation/stenosis] can be entered on study). Subjects with moderate valvular thickening should not be entered on study.
- Treatment refractory hypertension defined as a blood pressure of systolic  $> 140$  mmHg and/or diastolic  $> 90$  mm Hg which cannot be controlled by anti-hypertensive therapy.

4.2.10 A history or current evidence/risk of retinal vein occlusion (RVO) or central serous retinopathy (CSR) including:

- a. Presence of predisposing factors to RVO or CSR (e.g. uncontrolled glaucoma or ocular hypertension, uncontrolled hypertension, uncontrolled diabetes mellitus, or a history of hyperviscosity or hypercoagulability syndromes); or
- b. Visible retinal pathology as assessed by ophthalmic examination that is considered a risk factor for RVO or CSR such as:
  - i. Evidence of new optic disc cupping;
  - ii. Evidence of new visual field defects on automated perimetry;
  - iii. Intraocular pressure  $> 21$  mmHg as measured by tonography.

4.2.11 Known immediate or delayed hypersensitivity reaction or idiosyncrasy to drugs chemically related to the study treatments, their excipients, and/or dimethyl sulfoxide (DMSO).

AMEND #1: 2018-APR-06; AMEND #2: 2018-OCT-26

4.2.12 Pregnant or lactating women. Women of childbearing potential must have a negative serum pregnancy test within 14 days prior to registration. Men and women of childbearing potential who do not agree to use adequate contraception (intrauterine device, double barrier method of birth control; abstinence) prior to study entry, for the duration of the study participation and 4 months after last dose of study treatment. (Should a woman become pregnant or suspect she is pregnant, or should a man father a child, while participating in this study, she/he should inform the treating physician immediately.) *Note:* Hormonal-based methods (e.g. oral contraceptives) are not permitted as contraception due to potential drug-drug interactions with dabrafenib.

4.2.13 History of interstitial lung disease or active pneumonitis.

4.2.14 Any one brain metastases > 4 cm in maximal diameter, and/or presence of brain metastases of less than 1 cm.

4.2.15 Brainstem metastases.

4.2.16 Contraindications to MRI and/or Gadolinium contrast or stereotactic brain radiation therapy.

AMEND #1: 2018-APR-06; AMEND #2: 2018-OCT-26

5.0 PATIENT EVALUATION FLOWSHEET: PRE-TREATMENT, ON STUDY, AND AFTER TREATMENT

All patients entered on study must be evaluated according to the schedule outlined below with documentation submitted according to the schedule in Appendix III.

Required Investigations	Pre-study (≤ 14 days prior to registration)	Within 28 days prior to registration	Day 1 each cycle, and as clinically indicated	Every 8 weeks from date of registration	4 weeks after completion of protocol therapy	3 month follow-up (only required for pts without confirmed PD and ongoing toxicities  )
History and Physical Exam						
including: height, weight, Karnofsky Performance Status, clinical tumour measurements (if applicable)	X		X 		X	
Blood pressure, heart rate, temperature (assessed by medical personnel)	X		X 		X	X
Hematology*						
CBC, differential, platelets	X		X 		X 	X
Coagulation*						
PT/INR and PTT	X 					
Biochemistry*						
Sodium, potassium, chloride, bicarbonate, magnesium, calcium, albumin, alkaline phosphatase, ALT, AST, total bilirubin, blood glucose (random, unless abnormal then fasting required), creatinine and creatinine clearance  , LDH, total protein	X		X 		X 	X
Radiology						
CT thorax/abdomen/pelvis (contrast enhanced) and other scans as required to document all sites of disease		X 		X 	X 	X 
MRI of brain (required)		X 		X 	X 	X 
Other Investigations						
Pregnancy Test 	X					
EKG				as clinically indicated		
ECHO/MUGA 		X 				
Ophthalmologic exam				as clinically indicated		
Dermatology exam				as clinically indicated		
Adverse events 	X 		continuously			X 

*footnotes on next page*

* Pre-treatment blood draws and physical exams may be done up to two working days prior to treatment if necessary (e.g. Friday for treatment on Monday, or to accommodate holidays). In order to ensure that nadir counts are not missed, every effort should be made to do interim blood draws within 24 hours of the day specified in the protocol.
1. Every three months thereafter to follow adverse events felt related until resolved to $\leq$ grade 2.
2. Labs do NOT need to be repeated C1D1 but vital signs should be done on day 1 of each cycle, including cycle 1.
3. At 4 weeks then every 3 months thereafter to follow abnormal results felt related until resolved to $\leq$ grade 2.
4. Then as clinically indicated.
5. Creatinine clearance required if serum creatinine $\geq$ 1.5 ULN. To be measured directly by 24 hour urine sampling or calculated by Cockcroft Formula (see protocol Section 4.1.11).
6. To ensure comparability, baseline X-rays/scans/LVEF evaluation must be performed using identical techniques.
7. 35 days if negative.
8. $\pm$ 14 day window to aid in scheduling.
9. To be done additionally every 3 months thereafter until relapse or progression for patients with CR, PR, or SD response.
10. Patients with a CR or PR should have scans repeated after 4 weeks to confirm response.
11. For women of childbearing potential only. Required within 14 days prior to registration.
12. Adverse Events to be evaluated using the NCI Common Terminology Criteria for Adverse Events (see Appendix IV).
13. Within 7 days prior to registration; again within 24 hours prior to first treatment.

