1.2 Secondary Objectives

- Extra-cranial objective response rate and overall ORR.
- Duration of response.
- Intracranial and overall progression free survival.
- Overall Survival.
- To evaluate the safety and tolerability of the regimen using the CTCAE v.4.

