10.0 PROTOCOL TREATMENT DISCONTINUATION AND THERAPY AFTER STOPPING

10.1 Criteria for Discontinuing Protocol Treatment

Patients may stop protocol treatment in the following instances:

- Intercurrent illness which would, in the judgement of the investigator, affect assessments of clinical status to a significant degree, and require discontinuation of protocol therapy.
- Unacceptable toxicity as defined in Section 7.0.
- Tumour progression or disease recurrence as defined in Section 8.0.
- Request by the patient.
- Efforts should be made to maintain the investigations schedule and continue follow-up, even if patients discontinue protocol treatment prematurely and/or no longer attend the participating institution.

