10.2 Therapy After Protocol Treatment is Stopped

At the discretion of the investigator.

Note, patients with CNS progression that can be managed with additional SRS or whole brain radiotherapy can continue on dabrafenib and trametinib if there is no evidence of progression outside of the CNS and it is felt that continuation of systemic treatment may benefit the patient.

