10.3 Follow-up Off Protocol Treatment

All patients will be seen at 4 weeks after completion of protocol therapy. Thereafter, continued follow-up is not required for patients who go off protocol treatment with progressive disease, except to document ongoing toxicities (until resolved to  $\leq$  grade 2) and late toxicities (including second malignancies). For patients who go off protocol treatment with CR, PR, or SD ongoing, follow-up will be required every 3 months until relapse. Final report (Death Report) will be required on all patients. Due within 2 weeks of knowledge of death (see Appendix III - Documentation for Study).

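### After progression at any site the plan requires no brain MRI beyond the 4-week post-treatment scan, so intracranial PFS loses follow-up in patients whose progression is extracranial only

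*Combined protocol and SAP*

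**What the plan says.** Section 1.2 lists "Intracranial and overall progression free survival" among the secondary objectives, and Section 12.3 plans to evaluate intracranial PFS within each cohort of 20-25 patients.

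The Section 5.0 flowsheet schedules brain MRI at baseline, every 8 weeks from registration, and 4 weeks after protocol therapy ends. Beyond that, four places set the rule:

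- Section 5.0, footnote 9, attached to both the CT row and the brain MRI row: "To be done additionally every 3 months thereafter until relapse or progression for patients with CR, PR, or SD response".
- Section 5.0, heading of the last column: "3 month follow-up (only required for pts without confirmed PD and ongoing toxicities".
- Section 10.3: "continued follow-up is not required for patients who go off protocol treatment with progressive disease, except to document ongoing toxicities" and late toxicities.
- Appendix III, Follow-up Report row: the same release after progressive disease.

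Section 7.0 continues the drugs until progression or unacceptable toxicity. Section 10.2 makes one exception: "patients with CNS progression that can be managed with additional SRS or whole brain radiotherapy can continue on dabrafenib and trametinib", provided that there is no progression outside the CNS.

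Two general statements point the other way. Section 10.1 says "Efforts should be made to maintain the investigations schedule and continue follow-up, even if patients discontinue protocol treatment prematurely". Section 6.2 has all registered patients followed until death or until the coordinating group ends follow-up. Neither mentions brain MRI after progression.

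**The concern.** A patient whose brain disease is controlled but who progresses outside the brain has had no intracranial event. The imaging needed to detect one is no longer required after the 4-week scan. The opposite case, CNS progression alone, is accommodated by Section 10.2, but in that case the intracranial event has already been seen.

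The rationale in Section 2.0 is longer intracranial control, and intracranial PFS is the endpoint that would show it. If brain follow-up ends in a selected group, the reported curve depends on how those patients are handled. Nothing in Section 8 or Section 12 defines the intracranial PFS event, its censoring, or the role of extracranial progression. An analysis rule can be chosen later, but scans that were never done or never recorded cannot be recovered.

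**Working it through.** **1. Is there a figure in the plan to reproduce?** There is none for intracranial PFS: no event count, precision or power is given. The only design calculation is the Simon design for response in Section 12.3 (40% versus 60%, alpha = beta = 0.10). Continuing with more than 7/18 responses and succeeding with more than 22/46 gives an exact alpha of 0.0952 and power of 0.9004, so it reproduces. Best response is taken up to the end of treatment (Section 8.2.5), so post-treatment imaging does not enter this design.

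**2. Tracing one patient through the rules.** Intracranial PR, then extracranial progression at an 8-weekly assessment:

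- Section 7.0: drugs run until progression. The Section 10.2 exception does not apply, because the progression is outside the CNS.
- Section 5.0: one brain MRI 4 weeks after treatment.
- Footnote 9, the column heading, Section 10.3 and Appendix III: the patient left with progressive disease, so no later imaging or Follow-up Report is required, apart from toxicity.
- Intracranial PFS: no event yet. A Death Report is still required, so overall survival is not affected.

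**3. How many patients?** Inputs from the documents: 50 patients and 12-18 months of accrual plus 6 months of follow-up (Section 12.3); median overall PFS of 11.0 months on the drug pair (Section 2.0, a phase III population, not this one). Assumptions: exponential times, uniform accrual, no deaths, 30-50% of first progressions extracranial only, and all such patients leave treatment.

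Hazard: λ = ln 2 / 11.0 = 0.0630 per month.

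Proportion progressed by cut-off with accrual of A months: 1 − [exp(−6λ) − exp(−(A+6)λ)] / (Aλ).

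- A = 12: 1 − (0.685 − 0.322)/0.756 = 0.52
- A = 18: 1 − (0.685 − 0.220)/1.134 = 0.59

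Patients affected:

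- Low: 0.30 × 0.52 × 50 ≈ 8. High: 0.50 × 0.59 × 50 ≈ 15.
- Per cohort: 0.30 × 0.52 × 20 ≈ 3 to 0.50 × 0.59 × 25 ≈ 7.
- Ceiling if every patient progresses: 0.30 × 50 = 15 to 0.50 × 50 = 25.

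**4. Which way does the estimate move?** This is a simulation for illustration only. It assumes exponential intracranial and extracranial times, an any-site median of 11.0 months under independence, an extracranial share of the hazard of 30-70%, a Gaussian-copula correlation of 0-0.6, no deaths, and no credit for the 4-week scan. Probability of being free of intracranial progression at 12 months, for a 50% share:

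| Correlation | Full brain follow-up | Censored at extracranial PD | Extracranial PD as event |
|---|---|---|---|
| 0 | 68.5% | 68.4% | 46.9% |
| 0.3 | 68.5% | 71.3% | 50.9% |
| 0.6 | 68.5% | 74.5% | 55.4% |

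Over all shares, censoring is unbiased at zero correlation and about 2-7 points too high at correlations of 0.3-0.6. Counting extracranial progression as an event is about 5-33 points too low. Between 10% and 47% of intracranial progressions within 12 months fall after extracranial progression.

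**The case against.** The strongest reply is that the plan does not forbid the scans. One brain MRI is scheduled 4 weeks after treatment, Section 10.1 asks for efforts to keep the schedule, and Section 6.2 follows patients until death. Footnote 9 sits separately on the MRI row and Section 8.1 assesses the CNS separately, so one could read it as MRI until CNS progression. This disposes of the stronger statement that brain imaging stops at progression. It does not restore required imaging: Section 10.3 and Appendix III release patients with progressive disease specifically and without naming a compartment.

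Three further objections stand against stronger readings that a reader might infer:

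- **That the bias must lengthen intracranial PFS.** The documents do not fix the event or censoring rule, censoring is unbiased under independence, and one plausible rule shortens the estimate. Nor do they give evidence that brain relapse risk rises when the drugs stop; later therapy is at the investigator's discretion (Section 10.2).
- **That intracranial response duration is also truncated.** The listed endpoint is duration of response, and Section 8.3 names no compartment. If overall response is meant, extracranial progression properly ends it.
- **That 15-25 patients would be lost.** That requires every patient to progress. Section 2.0 also gives reasons why the brain might often fail first: about 50% new distant brain metastases after SRS alone, and intracranial responses lasting 20.1 and 28.1 weeks on dabrafenib alone. These come from other populations and treatments, so they do not settle the share.

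It is also fair that this concerns a secondary endpoint, in a non-randomised trial whose cohort and historical comparisons are descriptive (Section 12.2).

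**Conclusion.** The point holds for intracranial PFS. Four consistent places end required brain imaging, after one post-treatment scan, for patients who leave with progression at any site, and intracranial PFS is still running in those with extracranial progression only. Sections 10.1 and 6.2 point the other way in general terms and must be reconciled with Section 10.3.

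The estimate would be too long under informative censoring or undetected relapse if the progression risks are positively correlated, and too short if extracranial progression counts as an event. The documents do not settle which applies. About 8-15 of 50 patients would be affected by cut-off under the assumed 30-50% share and the 11.0-month median. Shorter PFS or longer follow-up raises this towards the 15-25 ceiling.

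A reader might go on to infer that the trial cannot support its expectation of longer intracranial control. That expectation is background rationale, not a tested hypothesis. The primary intracranial response rate, overall survival and the sample size are unaffected. This should be corrected, but it does not undermine the trial.

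**What to change.** Make footnote 9, Section 10.3 and the Follow-up Report row of Appendix III compartment-specific. For patients off treatment with extracranial but not intracranial progression, record the dates and results of brain MRIs done in routine care on the existing 3-monthly Follow-up Report, until intracranial progression or death. Align Sections 10.1 and 6.2 with this. No additional MRI needs to be mandated.

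In Section 12, define intracranial PFS as time to intracranial progression or death, keep it as the stated endpoint, and state its censoring rule. Add the cumulative incidence of intracranial progression with death as a competing event. Add a sensitivity analysis in which extracranial progression leading to treatment stop is also a competing event.

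The cost is a short amendment and some extra data entry, for roughly 8-15 patients under the assumptions above. Routine-care scans will sometimes be missing or off schedule, so report how many of these patients had brain imaging after leaving treatment. No sample-size figure changes.

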#### On-Treatment Evaluations

- Physical Exam: weight, Karnofsky Performance Status (Appendix I), clinical tumour measurements (if applicable): day 1 each cycle.
- Vital signs: blood pressure, heart rate, temperature: day 1 each cycle.
- Hematology & Biochemistry: day 1 each cycle.
- PT/INR and PTT: as clinically indicated.
- Radiology (MRI brain and CT chest, abdomen and pelvis): every 8 weeks.
- EKG, ECHO/MUGA, ophthalmology and dermatology exam: as clinically indicated.
- Adverse events: end of each cycle.

Duration of Protocol Treatment

Patients may stop protocol treatment in the following instances:

- Intercurrent illness which would, in the judgement of the investigator, affect assessments of clinical status to a significant degree, and require discontinuation of protocol therapy.
- Unacceptable toxicity as defined in Section 7.0.
- Tumour progression or disease recurrence as defined in Section 8.0.
- Request by the patient.

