8.2.3 *Target Lesions*. When more than one measurable tumour lesion is present at baseline all lesions up to *a maximum of 5 lesions total* (and a maximum of *2 lesions per organ*) representative of all involved organs should be identified as target lesions and will be recorded and measured at *baseline*. Target lesions should be selected on the basis of their size (lesions with the longest diameter), be representative of all involved organs, but in addition should be those that lend themselves to *reproducible repeated measurements*. Note that pathological nodes must meet the criterion of a short axis of  $\geq 15$  mm by CT scan and only the *short axis* of these nodes will contribute to the baseline sum. All other pathological nodes (those with short axis  $\geq 10$  mm but  $< 15$  mm) should be considered non-target lesions. Nodes that have a short axis  $< 10$  mm are considered non-pathological and should not be recorded or followed (see 10.2.4). At baseline, the sum of the target lesions (longest diameter of tumour lesions plus short axis of lymph nodes: overall maximum of 5) is to be recorded.

After baseline, a value should be provided on the CRF for all identified target lesions for each assessment, even if very small. If extremely small and faint lesions cannot be accurately measured but are deemed to be present, a default value of 5 mm may be used. If lesions are too small to measure and indeed are believed to be absent, a default value of 0 mm may be used.

8.2.4 *Non-target Lesions*. All non-measurable lesions (or sites of disease) plus any measurable lesions over and above those listed as target lesions are considered *non-target lesions*. Measurements are not required but these lesions should be noted at baseline and should be followed as “present” or “absent”.

8.2.5 *Response*.

All patients will have their BEST RESPONSE from the start of study treatment until the end of treatment classified as outlined below:

*Complete Response (CR)*: disappearance of *target* and *non-target* lesions. Pathological lymph nodes must have short axis measures  $< 10$ mm (*Note*: continue to record the measurement even if  $< 10$ mm and considered CR). Residual lesions (other than nodes  $< 10$ mm) thought to be non-malignant should be further investigated (by cytology specialized imaging or other techniques as appropriate for individual cases [ref RECIST 1.1]) before CR can be accepted. Confirmation of response is required in non-randomized studies.

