*Partial Response (PR)*: at least a 30% decrease in the sum of measures (longest diameter for tumour lesions and short axis measure for nodes) of target lesions, taking as reference the baseline sum of diameters. Non target lesions must be non-PD. Confirmation of response is required in non-randomized studies.

*Stable Disease (SD)*: Neither sufficient shrinkage to qualify for PR nor sufficient increase to qualify for PD taking as reference the smallest sum of diameters on study.

Progressive Disease (PD): at least a 20% increase in the sum of diameters of measured lesions taking as references the smallest sum of diameters recorded on study (including baseline) AND an absolute increase of  $\geq 5\text{mm}$ . Appearance of new lesions will also constitute progressive disease (including lesions in previously unassessed areas). In exceptional circumstances, unequivocal progression of non-target disease may be accepted as evidence of disease progression, where the overall tumour burden has increased sufficiently to merit discontinuation of treatment or where the tumour burden appears to have increased by at least 73% in volume. Modest increases in the size of one or more non-target lesions are NOT considered unequivocal progression. If the evidence of PD is equivocal (target or non-target), treatment may continue until the next assessment, but if confirmed, the earlier date must be used.

A single CNS lesion must increase by an absolute value of  $\geq 5\text{ mm}$  to be considered progression.

Radiation Necrosis versus Progressive Disease: Progression is not unequivocal if change in imaging is possibly due to radiation necrosis. If the treated lesion changes in such a way that radiation necrosis is suspected then follow-up scans are required. If no further growth or regression is observed then the response assessment should be stable disease rather than progressive disease. If a patient has surgery and pathology indicates radiation necrosis then this should be noted in the response assessment. For SRS treated lesions, an advanced imaging modality such as perfusion MR imaging, MR spectroscopy, or 18FLT or 18FDG positron emission tomography (PET) may be used as additional evidence of tumor progression or treatment effect/radionecrosis.

Corticosteroid Use and Clinical Deterioration:

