- a. An increase in corticosteroid dose alone, in the absence of clinical deterioration related to tumour, will not be used as a sole determinant of progression. Patients with stable imaging studies whose corticosteroid dose was increased for reasons other than clinical deterioration related to tumour do not qualify for stable disease or progression. They should be observed closely. If their corticosteroid dose can be reduced back to baseline, they will be considered as having stable disease; if further clinical deterioration related to tumour becomes apparent, they will be considered to have progression.
- b. The definition of clinical deterioration is left to the discretion of the treating physician, but it is recommended that a decline in the KPS from 100 or 90 to 70 or less, a decline in KPS of at least 20 points from 80 or less, or a decline in KPS from any baseline to 50 or less, for at least 7 days, be considered neurologic deterioration unless attributable to comorbid events, treatment-related toxicity, or changes in corticosteroid dose.

Table 1: Integration of Target, non-Target and New Lesions into Response Assessment:

Target Lesions	Non-Target Lesions	New Lesions	Overall Response	Best Response for this Category also Requires
Target lesions ± non target lesions				
CR	CR	No	CR	tumour nodes <10mm
CR	Non-CR/Non-PD	No	PR	
CR	Not all evaluated	No	PR	
PR	Non-PD/ not all evaluated	No	PR	
SD	Non-PD/ not all evaluated	No	SD	documented at least once $\geq$ 4 wks. from baseline
Not all evaluated	Non-PD	No	NE	
PD	Any	Any	PD	
Any	PD	Any	PD	
Any	Any	Yes	PD	
Non target lesions ONLY				
No Target	CR	No	CR	tumour nodes < 10mm
No Target	Non-CR/non-PD	No	Non-CR/non-PD	
No Target	Not all evaluated	No	NE	
No Target	Unequivocal PD	Any	PD	
No Target	Any	Yes	PD	
Note: Patients with a global deterioration of health status requiring discontinuation of treatment without objective evidence of disease progression at that time should be reported as "symptomatic deterioration". This is a reason for stopping therapy, but is NOT objective PD. Every effort should be made to document the objective progression even after discontinuation of treatment.				

For non-randomized trials, where confirmation of response is required, best overall response can be interpreted as follows:

Response: First Time Point	Subsequent Time Point	BEST Overall Response	Also Requires
CR	CR	CR	tumour nodes < 10mm
CR	PR	SD, PD or PR (see comment*)	

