CR	SD	SD provided minimum criteria for SD duration met, otherwise, PD	
CR	PD	SD provided minimum criteria for SD duration met, otherwise, PD	
CR	NE	SD provided minimum criteria for SD duration met, otherwise NE	
PR	CR	PR	
PR	PR	PR	
PR	SD	SD	
PR	PD	SD provided minimum criteria for SD duration met, otherwise, PD	
PR	NE	SD provided minimum criteria for SD duration met, otherwise NE	
NE	NE	NE	

\* may consider PR providing initial "CR" likely PR on subsequent review – then original CR should be corrected.  
Recurrence of lesion after true CR is PD.

Because CNS progression of disease may be masked by corticosteroids or manifest by neurological deterioration without radiological progression, the following ADDITIONAL parameters will be used:

Response Criteria for CNS Metastases

Criterion	CR	PR	SD	PD
Target lesions	None	$\geq 30\%$ decrease in sum LD relative to baseline	< 30% decrease relative to baseline but < 20% increase in sum LD relative to nadir	$\geq 20\%$ increase in sum LD relative to nadir*
Non-target lesions	None	Stable or improved	Stable or improved	Unequivocal PD*
New lesion(s)**	None	None	None	Present*
Corticosteroids	None	Stable or decreased	Stable or decreased	NA +
Clinical status	Stable or improved	Stable or improved	Stable or improved	Worse*
Requirement for response	All	All	All	Any +

\* Progression occurs when this criterion is met.

\*\* New lesion = new lesion not present on prior scans and visible in at least 2 projections. If a new lesion is equivocal, for example because of its small size, continued therapy may be considered, and follow up evaluation will clarify if it represents truly new disease. If repeat scans confirm there is definitely a new lesion, then progression should be declared using the date of the initial scan showing the new lesion. For immunotherapy-based approaches, new lesions alone to do not define progression (See "Guidance in the case of new lesion(s) while on immunotherapy").

+ Increase in corticosteroids alone will not be taken into account in determining progression in the absence of persistent clinical deterioration.

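### Best response closes at the end of treatment, but the scan labelled as confirming a response and the evaluability rule both reach past that point

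*Combined protocol and SAP*

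**What the plan says.** - **Window.** Section 8.2.5: "All patients will have their BEST RESPONSE from the start of study treatment until the end of treatment classified as outlined below".
- **Confirmation.** The same section, under both CR and PR: "Confirmation of response is required in non-randomized studies". Its table is introduced with "For non-randomized trials, where confirmation of response is required, best overall response can be interpreted as follows". It pairs a first time point with a subsequent one and does not say that the second must fall on treatment. A response followed by a non-evaluable time point becomes "SD provided minimum criteria for SD duration met, otherwise NE".
- **The labelled confirming scan.** Section 5.0, footnote 10: "Patients with a CR or PR should have scans repeated after 4 weeks to confirm response". The footnote mark appears only on the CT and MRI cells of the column headed "4 weeks after completion of protocol therapy".
- **On-treatment scans.** The summary of on-treatment evaluations has "Radiology (MRI brain and CT chest, abdomen and pelvis): every 8 weeks". In the flowsheet these cells carry only footnote 8, a plus or minus "14 day window to aid in scheduling".
- **Evaluability.** Section 8.1.2 asks for at least one cycle of therapy and a re-evaluation of disease. It does not require the re-evaluation to take place on treatment.
- **After stopping.** Section 10.1 asks sites to try to keep to the investigation schedule after a premature stop. Section 8.5 puts assessments on a calendar schedule. Footnote 9 continues scans every 3 months for patients in CR, PR or SD.

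**The concern.** Confirmed intracranial response to drug plus SRS is the primary endpoint. Three rules bear on whether a patient counts as a responder, and they do not share an end point. The best-response window shuts when treatment ends, the scan described as confirming a response comes 4 weeks later, and the evaluability rule has no such limit. No sentence says whether a scan after the last dose can establish or confirm a response.

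The patients concerned stop drug without progression, for example for toxicity. If the window is applied strictly, some of them stay in the denominator while the scan that shows their response is disregarded. Section 11.1 reports both local and central radiology review, so the two could also classify the same patient differently for want of a rule.

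**Working it through.** **1. Which patients are exposed.** I take the end of treatment to be permanent discontinuation of protocol treatment, as the End of Treatment Report in Appendix III does. Scans fall nominally at weeks 8 and 16 from registration, each within 2 weeks either way.

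- First scan: weeks 6 to 10. Second scan: weeks 14 to 18.
- Gap between consecutive scans: 8 − 2 − 2 = 4 weeks at least, 8 + 2 + 2 = 12 weeks at most. The next 8-weekly scan therefore always meets a 4-week minimum.

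*Group A: stops before any on-treatment scan shows a response.* Take a stop at week 6 and a post-treatment MRI at week 10 showing PR. The patient has had more than one 28-day cycle and a re-evaluation, so is evaluable under Section 8.1.2. The PR lies outside the Section 8.2.5 window and is excluded by the stated rule.

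*Group B: stops between the first response scan and the next scheduled one.* Take PR at week 8, a stop at week 10 and PR again on the post-treatment MRI at week 14. The first PR is inside the window and the second is 6 weeks later. The table reads PR then PR, which is PR. Only if the window is also applied to the confirming scan is the patient unconfirmed.

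*Not exposed:* any responder with a second qualifying scan on treatment.

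Footnote 10 can mean that the post-treatment scan is itself the repeat, or that a CR or PR found on it should be repeated 4 weeks later. On either reading the confirming scan falls after treatment has ended.

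**2. The plan's own design.** Section 12.3 gives a null ORR of 40%, a target of 60%, alpha and beta of 0.10, more than 7 responses in 18 at stage one, and 22/46 at stage two. For response rate p:

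P(pass | p) = Σ (x = 8 to 18) P[Bin(18, p) = x] × P[Bin(28, p) ≥ 23 − x]

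- p = 0.40: 0.0952. p = 0.60: 0.9004.
- An exhaustive search for the optimal Simon design returns the same 7/18 and 22/46, so the plan's figure reproduces with success at more than 22.
- Reading 22/46 as at least 22 would give 0.1444 and 0.9222, which breaks the stated alpha.

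**3. Sensitivity to lost responses.** Let f be the share of true responses not counted. The protocol gives no value for f, so the range is an assumption. Recorded ORR = 0.60 × (1 − f). Expected true responses in 46 = 46 × 0.60 = 27.6.

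| f | Expected responses lost (27.6 × f) | Recorded ORR | P(pass) |
|---|---|---|---|
| 0% | 0 | 60% | 0.900 |
| 5% | 1.4 | 57% | 0.819 |
| 10% | 2.8 | 54% | 0.703 |
| 15% | 4.1 | 51% | 0.559 |

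The calculation keeps every affected patient in the 46 as a non-responder.

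**The case against.** The strongest reply is that the protocol can be read so that every passage has effect. The confirmation table does not require the second scan to be on treatment, and the placement of footnote 10 is itself evidence that a post-treatment scan is meant to confirm. Sections 8.5 and 10.1 keep scans coming after an early stop. On that reading Group B loses no one. This stands, and Group B is therefore an ambiguity only.

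A reader might go further and infer that responders who stop early for toxicity cannot be confirmed at all, or that staying on drug until about weeks 14 to 18 is a hidden condition for being a responder. The documents do not support that. The next 8-weekly scan can confirm without carrying the label, and nothing bars the later scan. Nor does the row for a response followed by a non-evaluable time point apply to a patient whose post-treatment MRI was done and shows PR.

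The exposed groups are also small by construction. Table 2 in Section 7.1.3 lists several toxicities for which trametinib stops permanently while dabrafenib may continue, so intolerance of one drug need not end protocol treatment.

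For Group A it can be argued that if the post-treatment MRI is not a valid re-evaluation, the patient is inevaluable and falls within the 10% allowance of Section 12.3 instead of counting as a failure. But Section 8.1.2 contains no such restriction. As written, the patient is evaluable and the response is excluded.

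**Conclusion.** Section 8.2.5 conflicts with footnote 10 and with Section 8.1.2 on the primary endpoint, and the conflict should be resolved. It excludes by rule a first CR or PR seen only after drug has stopped in an otherwise evaluable patient. It leaves open whether a post-treatment scan confirms a response first seen on treatment, although the text favours that it does.

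Under the literal reading, evaluable patients can only move from responder to non-responder, so any bias in intracranial ORR is downward. A reader might take the figures 0.82, 0.70 and 0.56 as the plan's actual power. They are not. They assume loss rates that the documents do not give and the strictest reading of the window. If no response is lost, the chance of passing stays at 0.90. They show only that, with the boundary at 22 of 46, one to four lost responses would matter.

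**What to change.** In Section 8.2.5, define the window for best intracranial response as running from the start of study treatment to the earlier of first intracranial progression or the start of other anti-cancer therapy. State that it includes the post-treatment MRIs already scheduled.

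In Section 8.2.5 and footnote 10, state that a CR or PR is confirmed by any scan at least 4 weeks later within that window, including the next 8-weekly scan.

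The cost is wording in two places. No scans are added, since the flowsheet already requires the 4-week and 3-monthly imaging for patients who stop without progression. The downside is that a few responses will first be credited after drug has stopped. List them separately and report intracranial ORR with and without them. The change is best made before responses are classified.
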